4.2 Analysis populations

4.2.1 Modified intention-to-treat (mITT) population

In the mITT analysis, patients will be analyzed based on their randomization allocations. If patients randomly assigned to the IA group receive EA during surgery, they will be analyzed within the IA group in the mITT analysis. If patients randomly assigned to group EA receive IA during surgery, they will be analyzed according to group EA. Patients who meet the exit criteria after randomization won't be included in the mITT population.

4.2.2 Per-protocol (PP) population

In PP analysis, only cases treated strictly in accordance with random groups and assigned treatment plans will be included. Patients who haven't been treated with a randomly assigned protocol will be excluded from the per-protocol analysis.

4.2.3 As-treated (AT) population

In the AT analysis, we'll analyze patients according to the actual treatment they received instead of the allocated plan for random groups.

4.3 Analysis of endpoints

The analyses of primary endpoint and secondary endpoints will be conducted in mITT population, PP population and AT population.

Analyses for the primary outcome variable will be unadjusted. In analyzing the primary outcomes, the rate of overall SSI will be reported as frequencies and percentages. We will calculate the absolute risk differences and the corresponding 95% confidence interval (CI) between two groups. If the absolute risk differences and the corresponding 95% CI are within the non-inferiority margin (<5%), non-inferiority is established. If not, IA is not non-inferior to EA.

The independent risk factor of the primary endpoint will be analyzed in the AT population. High-risk variables identified through univariable analysis and clinical experience will be included in the multivariable analysis. Multivariable logistic regression will be employed to identify independent risk factors for SSI. The effect size will be estimated using odds ratios (ORs) with 95% confidence intervals.

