12.1 Method for determining sample size

This study is a multicenter, randomized, controlled, noninferiority trial specifically designed for patients within the age range of 18 to 80 years old who are diagnosed with left-sided colon cancer. We adjusted the sample size according to our latest published multicenter retrospective data(19). We expected that the incidence of overall surgical site infection following extracorporeal anastomosis left colon cancer surgery stands at 13.3%, while the incidence of SSI after intracorporeal anastomosis is 8.0%. When there is an absolute risk difference in the SSI rate of more than 5% within 30 days after surgery, intracorporeal

anastomosis is regarded as inferior to extracorporeal anastomosis. Consequently, the sample size for this study is calculated based on non-inferiority, considering an absolute risk difference of 5%, a one-sided level of significance of 0.025, a ratio of 1:1, a power of 0.80, and a 20% drop-out rate. In total, 350 patients are required for this study, with 175 patients in the experimental group and an equal number of 175 patients in the control group.

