The STARS trial is a multicenter, randomized, single-blind, non-inferiority study designed to compare the incidence of surgical site infection (SSI) following intracorporeal anastomosis (IA) versus extracorporeal anastomosis (EA) in patients undergoing surgery for left colon cancer. The primary objective of this trial is to determine whether IA is non-inferior to EA in terms of SSI rates within 30 postoperative days. While the aims, hypotheses, and design of the STARS trial have been detailed elsewhere, this statistical analysis plan (SAP) will focus on the forthcoming analysis and presentation of the trial data. This SAP is conducted based on the study protocol version 2.1. The comprehensive study design, including the primary and secondary endpoints, along with the methods for determining sample size and the approach to data management, are integral to the SAP and are critical for understanding the trial's methodology and interpretation of results.

2 Study design and objectives

This is a prospective, multicenter, non-inferiority, two-arm, single-blind, randomized controlled study. The study aims to investigate the effects of intracorporeal anastomosis and extracorporeal anastomosis in laparoscopic-assisted radical left hemicolectomy on surgical site infection. It also examines the difference in postoperative recovery, safety, oncology outcomes and survival. The trial was prospectively registered in clinicaltrial.gov (NCT04201717) and the study protocol (version 1.0) has been previously published,(1) and minor revisions has been made in study protocol version 2.0 and version 2.1. Details of exclusion criteria and study treatments can be found in study protocol version 2.1.

3 Sample size

The sample size is determined based on the rate of SSI. Based on our multicenter retrospective data,(2) we estimated the incidence of overall SSI following EA in laparoscopic left hemicolectomy stands at 13.3%, while the incidence of SSI after IA is 8.0%. When there is an absolute risk difference in the SSI rate of more than 5%

within 30 days after surgery, IA is regarded as inferior to EA. Consequently, the sample size for this study is calculated based on non-inferiority, taking into account an absolute risk difference of 5%, a one-sided level of significance of 0.025, a ratio of 1:1, a power of 0.80, and a 20% drop-out rate. In total, 350 patients are required for this study, with 175 patients in the IA group and an equal number of 175 patients in the EA group.

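### The trial is sized on a 5.3-point benefit of intracorporeal anastomosis, but no error-controlled superiority step follows non-inferiority, although adding one is free

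*Combined protocol and SAP*

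**What the plan says.** **Objective.** SAP 1 and protocol v2.1, 4.1 describe a non-inferiority trial of IA against EA. Neither promises a superiority claim.

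**Sizing.** SAP 3 states: "we estimated the incidence of overall SSI following EA in laparoscopic left hemicolectomy stands at 13.3%, while the incidence of SSI after IA is 8.0"%. The other inputs are "a one-sided level of significance of 0.025, a ratio of 1:1, a power of 0.80, and a 20% drop-out rate", giving 350 patients, 175 per arm. Protocol v2.1, 12.1 has the same figures.

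**Margin.** Protocol 12.1 introduces it with "When there is an absolute risk difference in the SSI rate of more than 5% within 30 days after surgery", and the matching sentence in SAP 3 ends "within 30 days after surgery, IA is regarded as inferior to EA". Neither sentence says in which direction the difference is taken.

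**Decision rule.** SAP 4.3 and protocol 12.3.1 share one sentence: "If the absolute risk differences and the corresponding 95% CI are within the non-inferiority margin (<5%), non-inferiority is established". The only alternative is that IA is not non-inferior. SAP 4.5 adds that the interval is compared with 5%. None of these places gives the order of subtraction, names the confidence limit that decides, or adds a further step if the interval also excludes zero.

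**Other comparisons of IA and EA on SSI.**
- Protocol 3.2.2 lists SSI among the postoperative complications, and SAP 4.6 compares complication subtypes between groups.
- SAP 4.5 includes the intervention as a candidate factor for overall SSI, in the as-treated population.
- SAP 4.5 also compares the SSI components, without reference to the margin.
- SAP 4.1 sets two-sided 0.05 for all tests. No multiplicity control is stated.

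**Subgroup gate.** SAP 4.7 runs subgroup analyses only if the mITT interval is not within the margin.

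**The concern.** The planning assumption is that IA lowers SSI, and the protocol introduction cites the need to reduce SSI rates. Yet if the trial shows a reduction, the primary analysis has no pre-specified way to say so with controlled error. A benefit claim would then rest on one of three things: a reading of the interval that was not planned, an uncorrected secondary test of SSI as one complication among many, or the as-treated model. The last does not preserve randomisation. It counts IA patients who cross over as EA, and its covariates are chosen after univariable analysis.

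Two wording matters touch the same rule. The direction and the deciding limit are left to inference, and the subgroup gate inherits this. The sample-size sections speak of IA being inferior, whereas the decision rule speaks only of non-inferiority not being met. A reader is also not told that the 80% power depends on a true benefit.

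**Working it through.** **Inputs** (SAP 3; protocol v2.1, 12.1): EA 0.133, IA 0.080, margin 0.05, one-sided alpha 0.025 (z = 1.960), power 0.80 (z = 0.842), drop-out 20%.

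**1. Reproduce the plan's sample size.** With unpooled variance, SSI being an adverse outcome:
- Variance sum: 0.133 × 0.867 + 0.080 × 0.920 = 0.1153 + 0.0736 = 0.1889.
- Distance: margin plus assumed benefit = 0.05 + (0.133 − 0.080) = 0.103.
- n = (1.960 + 0.842)² × 0.1889 / 0.103² = 139.8, so 140 evaluable per arm.
- 140 / (1 − 0.20) = 175 per arm, 350 in total. This matches the plan exactly.

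The match uses a one-directional distance of 10.3 points, so the sizing treats the margin as an upper bound on IA minus EA and credits IA with a 5.3-point benefit.

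**2. Expected interval at the planning rates, 140 per arm.** SE = √(0.1889/140) = 0.0367. Half-width = 1.96 × 0.0367 = 0.072. IA minus EA: −5.3 ± 7.2, that is −12.5 to +1.9 points.

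**3. Power of the directed non-inferiority rule** (upper limit below +5). Φ(0.103/0.0367 − 1.96) = 0.80. Exact binomial enumeration with Wald intervals gives 0.81. So 350 is unchanged when the rule is written out.

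**4. Power of a superiority step on the same interval** (upper limit below 0).
- 140 per arm: Φ(0.053/0.0367 − 1.96) = 0.30.
- 175 per arm (no drop-out), SE 0.0329: Φ(0.053/0.0329 − 1.96) = 0.36.

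An upper limit below 0 is also below +5, so these successes are a subset of those in step 3. A trial powered at 80% for superiority would need 531 evaluable per arm, or 664 per arm and 1,328 in total with 20% drop-out.

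**5. Alpha.** Both steps use the same upper limit. A false claim at either step requires that limit to fall below the true difference, which has probability 0.025 nominally. The second step therefore adds no error.

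**6. Non-inferiority power if the true rates are equal.** Φ(0.05/SE − 1.96), with SE = √(2p(1 − p)/n):

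| True rate in both arms | 140 per arm | 175 per arm |
|---|---|---|
| 13.3% | 23% | 28% |
| 8.0% | 34% | 41% |

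By subtraction, the margin would be missed in 66–77% of trials of truly equal techniques with 140 per arm, and in 59–72% with 175.

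**7. What a symmetric reading would do.** If the whole interval had to lie between −5 and +5, success at the planning rates with 140 per arm would have probability about 0.001%, by exact enumeration.

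**The case against.** The strongest reply is that the trial does what it says. The objective is non-inferiority, the rule answers that question, and a superiority step with 30–36% power is not something the design owes. This stands: the missing step is an opportunity, not an error.

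A reader might go further and infer that a benefit could never be claimed. The documents do not support that. The two-sided 95% interval is reported in any case, and overall SSI is compared between IA and EA in the as-treated risk-factor analysis. What is missing is narrower: a pre-specified, gated step in mITT.

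A reader might also infer that the plan's expected result would fail its own rule or count as inferior, because 5.3 exceeds 5 and the lower limit of −12.5 lies outside ±5. Taken literally and without sign, the wording allows this. But the parenthesis in the rule asks only for values below 5%, the design is non-inferiority at a one-sided 0.025, and 350 reproduces exactly with the one-directional distance. Together these show that the upper limit is meant. The direction point is a drafting clarification.

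The word inferior appears in the sample-size sections, where it describes the margin; the decision rule itself says only that IA is not non-inferior. The rewording is therefore a matter of consistency.

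**Conclusion.** The point holds as a free improvement, with clarifications attached. The plan is sized on a 5.3-point benefit of IA but has no error-controlled superiority step in mITT, and its other planned tests of IA against EA on overall SSI are ungated. A fixed-sequence step would show superiority in about 30% of trials with 140 evaluable per arm, or 36% with 175, if the planning rates are true.

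Two overstatements should be avoided. The 80% does not come wholly from the assumed benefit, because power at equal rates is 23–41% across the cases above and not zero. Nor does the 30% come on top of the 80%; it lies inside it.

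The figures rest on the plan's rates, normal approximations with unpooled variance, and either the full 20% drop-out or none. The no-alpha-cost argument requires the step to be fixed before unblinding; added later, it would be post hoc.

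**What to change.** Before unblinding, amend SAP 4.3 and 4.5 and protocol 12.3.1 along these lines:

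- *The difference is IA minus EA in the mITT population.*
- *Step 1: non-inferiority is shown if the upper limit of the two-sided 95% CI is below +5 points. There is no condition on the lower limit.*
- *Step 2, only if Step 1 is met: superiority is shown if the same upper limit is below 0.*

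As clarifications:

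- **SAP 4.7:** tie the subgroup gate to the Step 1 upper-limit rule, so that a strongly favourable IA result cannot trigger it.
- **Protocol 12.1 and SAP 3:** replace the statement that IA is inferior with 'non-inferiority not shown', and give the difference the same direction.
- **Protocol 12.1 and SAP 3:** add that the 80% power holds at a true 5.3-point benefit, and that at equal rates it is 23–34% with 140 per arm (28–41% with 175).

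The cost is wording only. Alpha is unchanged, no patients are added, and the sample size stays 350. The power statement becomes less flattering.

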4.4 Baseline Characteristics

The following baseline characteristics will be presented in mITT, PP and AT population:

- Sex, categorical variable;
- Age, continuous variable, measured in years;
- Body Mass Index, continuous variable, measured in kg/m²;
- American Society of Anesthesiologists grading, categorical variable
- Eastern Cooperative Oncology Group performance status score, categorical variable;
- Tumor site, categorical variable, classified as distal transverse colon (distal 1/2 of transverse colon), splenic flexure of colon (junction of transverse colon and descending colon), descending colon (descending colon and the junction of sigmoid colon and descending colon), and proximal sigmoid colon (proximal 1/3 of sigmoid colon);
- NRS2002 score, continuous variable, measured in points
- Parenteral prophylactic antibiotics, categorical variable;
- Mechanical bowel preparation, categorical variable;
- Oral antibiotic bowel preparation, categorical variable;
- Postoperative antibiotic use time, categorical variable, divide by ≥ 3 days and < 3 days;
- Clinical T stage, categorical variable;
- Clinical N stage, categorical variable;
- Clinical TNM stage, categorical variable;

4.5 Primary endpoint

The primary endpoint in this trial is surgical site infection (SSI) within 30 postoperative days. Cases that fail to complete the 30-day follow-up are treated as missing data. The SSI will be compared between groups in the mITT population, PP population, and AT population.

- Overall SSI, Categorical variable. The absolute risk differences and the corresponding 95% CI between two groups will be calculated. The 95% CI will be compared with the non-inferiority margin (5%).

The subtypes of SSI (Superficial or deep incisional SSI, and Organ/space SSI) will also be compared between the two groups. However, their 95% confidence interval will not be compared with the non-inferiority margin.

The independent risk factors for overall surgical site infection (SSI) will be analyzed in the AT population. In univariable analysis, continuous variables will be converted to categorical variables. Chi-square tests or Fisher's exact tests will be employed. The key variables are as follows.

- Sex (male, female);
- Age (≤ 65 years, > 65 years);
- Body Mass Index ($\leq 24 \text{kg/m}^2$, $> 24 \text{kg/m}^2$);
- American Society of Anesthesiologists grading (I, II, III);
- Eastern Cooperative Oncology Group performance status score (0, 1, 2);
- Tumor site (distal transverse colon, splenic flexure of colon, descending colon, and proximal sigmoid colon);
- NRS2002 score (≤ 2 points, > 2 points);
- Parenteral prophylactic antibiotics (Yes, No);
- Mechanical bowel preparation (No, only enema, only oral laxative, enema plus oral laxative);
- Oral antibiotic bowel preparation (Yes, No);
- Postoperative antibiotic use time (≥ 3 days, < 3 days);

- Pathological TNM stage (0, I, II, III);
- Overflow of intestinal contents during anastomosis (Yes, No);
- Operating time (≤ 180 mins, > 180 mins);
- Blood loss during operation (≤ 100 ml, > 100 ml);
- Blood transfusion during operation (Yes, No);
- Prophylactic enterostomy (Yes, No);
- Anastomosis methods (Side-to-side anastomosis, End-to-side anastomosis, End-to-end anastomosis)
- Intervention (intracorporeal anastomosis, extracorporeal anastomosis)

Factors clinically relevant to SSI after univariable analysis will be included in multivariable analysis. Logistic regression will be used in multivariable analysis to identify independent risk factors for SSI. The effect size will be estimated using odds ratios (ORs) with 95% confidence intervals.

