Intervention Methods	
Intracorporeal anastomosis group: Total laparoscopic technology is used. The tumor is resected according to surgical specifications for radical colon cancer surgery. Mesentery resection is performed under laparoscopy, and anastomosis is completed under laparoscopy. A small incision is made to extract the specimen.
 
Extracorporeal anastomosis group: Traditional laparoscopy-assisted technology is used. The tumor is resected according to surgical specifications for radical colon cancer surgery. A small incision is made in the middle of the abdomen to trim the mesentery, remove the specimen, and complete the anastomosis operation.

Primary Outcome Measures	The primary endpoint of this study was the surgical site infection within 30 days after surgery.
Follow-up Plan	The follow-up period for the primary endpoint was within 30 days after surgery. Follow-up is done through in-patient observation, outpatient consultations, and telephone inquiries. On the 30th day after surgery,

	
patients are required to return to the hospital for blood routine, liver function, kidney function, urinary routine, lung CT, and abdominal CT examinations. It also documents the patient's surgery-related complications and grades over this period, as well as solutions.
 
The total follow-up time for patients after surgery is 5 years. For patients with recurrent tumors, follow-up should continue for at least 3 years after recurrence or metastasis is discovered or until death.

Sample Size	350 cases
Statistical Methods	
1 Full analysis set
 
A comparative analysis of the primary outcomes will be conducted based on “modified intention-to-treat (mITT)”. In the mITT analysis, patients will be analyzed according to their randomization allocations.
 
2 Per-protocol analysis
 
In per-protocol analysis, only cases treated strictly in accordance with random groups and assigned treatment plans will be included. Patients who haven't been treated with a randomly assigned protocol will be excluded from the analysis.
 
3 As-treated analysis set
 
In the as-treated analysis set, we'll analyze patients according to the actual treatment plan they received instead of the allocated plan for random groups.

TABLE OF CONTENTS

1. Title.....	8
2. Introduction	8
3. Study Purpose and Endpoint.....	8
3.1 Study purpose	9
3.1.1 Main study purpose:	9
3.1.2 Secondary study purpose.....	9
3.2 Study endpoint.....	9

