Fig. 5 A Side-to-end anastomosis. It can be completed by inserting a circular stapler through the anus. Alternatively, it can be done by inserting the circular stapler through the end of the proximal colon and then using another linear stapler to close the end of the proximal colon after anastomosis. Hand sewing is also permitted. B end-to-end anastomosis. It can be completed by inserting a circular stapler through the anus. Alternatively, it can be done by sewing it by hand.

Table 1 The time point and assessments of the STARS study

Time point	Study period		Follow-up (month)					
	Screening	Treatment	1	12	24	36	48	60
Informed consent	✓							
Inclusion criteria	✓							
Exclusion criteria	✓	✓	✓	✓	✓	✓	✓	✓
Baseline data	✓							
Blood test	✓							
Tumor marker test	✓							
Chest CT	✓							
Pelvic MRI	✓							
Abdominal CT	✓		✓					
Electrocardiogram	✓							
Colonoscopy	✓							
Surgery		✓						
Complications		✓	✓					
Recurrence/death			✓	✓	✓	✓	✓	✓

7.3 Concurrent treatment and follow-up.

Postoperative chemotherapy is recommended according to the NCCN guidelines for colon

cancer treatment. The post-operative follow-up period must be in accordance with the time specified in this study (Table 1). Each participant will be followed until recurrence or death over a period of 5 years after the scheduled surgery.

The follow-up period for the primary endpoint is within 30 days after surgery. Follow-up will be conducted through in-patient observation, outpatient consultations, and telephone inquiries. SSI presence will be assessed daily during hospitalization and weekly after discharge. At least two surgeons perform SSI surveillance. The outcome assessors are trained on the Centers for Disease Control and Prevention (CDC) definitions of SSI to produce good inter-rater reliability for the assessment of SSI. If SSI is suspected during follow-up, CT or abdominal ultrasonography will be done. All patients will have an abdominal or pelvic CT on the 30th day after surgery. If the CT shows evidence of SSI, the radiologist and surgeon will assess whether there is an SSI.

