12.3.2 Secondary endpoint analysis

The analysis of the secondary endpoints will be carried out in the mITT population. In the analysis of secondary endpoints, categorical variables will be reported as frequencies and percentages. Groups will be compared using the χ^2 test or Fisher's exact test. Absolute risk differences and the corresponding 95% CI will be calculated. Continuous variables will be described as mean \pm standard deviation or median (quartile). Groups will be compared using the t-test or Mann-Whitney U test, as appropriate. Hodges-Lehmann method will be used to calculate the difference in median and the corresponding 95% CI.

The comparison of 3-year DFS and 3-year OS between the two groups will utilize the Kaplan-Meier curve and the Cox proportional risk model. Relevant risk factors will be adjusted in Cox proportional risk model.

The missing data in this trial is expected to be minimal. If it occurs, it will be treated as censored data and not imputed. All statistical tests were 2-sided, and statistical significance was set at $P < 0.05$. All statistical analyses were performed using R or SPSS.

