4.7 Subgroup analysis

The subgroup analysis will be carried out only if the primary endpoint in the mITT population do not reach the non-inferiority margin. If the 95% CI of SSI is not within the non-inferiority margin, the primary endpoint will be summarized within the following subgroups.

- Sex (male, female);
- Age (≤ 65 years, > 65 years);
- Body Mass Index ($\leq 24 \text{ kg/m}^2$, $> 24 \text{ kg/m}^2$);
- Tumor site (distal transverse colon or splenic flexure of colon, descending colon,

proximal sigmoid colon);

- NRS2002 score (≤ 2 points, > 2 points);
- Mechanical bowel preparation (Yes, No);
- Oral antibiotic bowel preparation (Yes, No);
- Postoperative antibiotic use time(≥ 3 days, < 3 days);
- Operating time (≤ 180 mins, > 180 mins);

Subgroup analyses will be performed using mITT population. If intracorporeal anastomosis is proven to be noninferior to extracorporeal anastomosis regarding SSI, subgroup analysis will not be performed.

5 Missing data

Missing primary endpoint data will be treated as censored data and won't be imputed during analysis. Other missing data won't be imputed either. The missing data will be stated in the tables.

6 Interim analyses

No interim analyses are planned in this study.

7 Timing of analysis

We will conduct an analysis of the study's primary endpoint and publish the relevant findings after enrollment is completed and all patients have completed the first month of follow-up after surgery. When all patients complete 5 years of follow-up, the results involving survival data will be analyzed again, and the relevant research results will be published.

Reference

1. He L, Li M, Zhang J xin, Tong W hua, Chen Y, Wang Q. Surgical site infection after intracorporeal anastomosis for left-sided colon cancer: study protocol for a non-

inferiority multicenter randomized controlled trial (STARS). *Trials*. 2022 Nov 22;23(1):954.

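### SAP 4.5 makes completed follow-up, not known SSI status, the test for a missing primary endpoint, so read literally a documented SSI can be deleted

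*Combined protocol and SAP*

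**What the plan says.** The endpoint is any SSI within 30 postoperative days (protocol version 2.1, 3.2.1). Protocol 7.3 sets the surveillance: "SSI presence will be assessed daily during hospitalization and weekly after discharge".

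SAP 4.5 defines missingness: "Cases that fail to complete the 30-day follow-up are treated as missing data". SAP 5 adds: "Missing primary endpoint data will be treated as censored data", without imputation, and "The missing data will be stated in the tables". Protocol 12.3.2 has matching wording, "If it occurs, it will be treated as censored data and not imputed", after the statement "The missing data in this trial is expected to be minimal".

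The primary analysis is an unadjusted absolute risk difference with a 95% CI, compared with a 5-point margin in the mITT, PP and AT populations (SAP 4.3 and 4.5). Censoring times are given only for DFS and OS (SAP 4.6).

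Three other rules bear on the same patients. Inability to complete the study plan and follow-up, for unspecified reasons, is exit criterion 5 (protocol 5.3). Patients who meet an exit criterion after randomization leave mITT (protocol 12.2.1, SAP 4.2.1). Data of withdrawn patients are not used (protocol 5.3 and 7.4).

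**The concern.** A 30-day binary endpoint is settled once the event occurs. A patient with an SSI on day 6 who is then lost has a known outcome, yet the SAP's test is whether follow-up was completed. No passage exempts a documented SSI, and the completion rule is attached to the endpoint itself, so none of the three populations is shown to keep the event. On the same literal reading a patient who dies before day 30 is also missing.

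At stake is whether a recorded primary event counts, which should not be left to interpretation after the data are seen. If SSI patients are lost more often than others, equally in both arms, the difference shrinks towards zero; when IA is truly worse, that favours a non-inferiority claim. If they are lost less often, it grows. Loss that differs by arm moves it either way.

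**Working it through.** **Plan's own figure.** Inputs from SAP 3: EA 13.3%, IA 8.0%, margin 5 points, one-sided 0.025, power 0.80, drop-out 20%. n = (1.960 + 0.842)² × (0.133×0.867 + 0.080×0.920) / (0.05 + 0.053)² = 7.849 × 0.1889 / 0.01061 = 139.8, so 140 per arm; 140/0.80 = 175; total 350. It reproduces. The point below does not change it.

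**One patient through the text.** SSI on day 6, no contact after day 14. Protocol 3.2.1: event. SAP 4.5: missing. SAP 5: censored. SAP 4.3 needs a numerator and a denominator, and censoring supplies neither, so the patient drops out of both. Protocol 5.3(5) with SAP 4.2.1: also outside mITT.

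**Size, under assumed loss.** The documents give no rate of SSI followed by loss, so everything here except the SSI rates, the margin and 175 per arm is an assumption. True rates are put at the margin: IA 18.3%, EA 13.3%. There is no loss before day 7; 5% of SSI-free patients are lost between days 7 and 30 (daily hazard λ = −ln(0.95)/23 = 0.00223). SSI onset is uniform over days 3 to 20. After SSI the hazard is fλ.

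Share of SSI patients who complete: c = mean of exp(−λ·pre − fλ·post), with pre = max(T,7) − 7 and post = 30 − max(T,7). This gives c = 0.950 (f = 1), 0.913 (f = 2), 0.969 (f = 0.5). Per arm, k = p·c + (1−p)·0.95, q = p·c/k, n = 175k. With d = q(IA) − q(EA) and unpooled SE, P(claim) = Φ((0.05 − d)/SE − 1.96).

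Example, f = 2 in both arms. IA: k = 0.183×0.9126 + 0.817×0.95 = 0.9432, q = 17.71%. EA: k = 0.9450, q = 12.84%. d = 4.86, SE = 3.95, P = Φ(0.035 − 1.960) = 2.71%.

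| Loss rate after SSI | Recorded SSIs deleted, IA / EA | Apparent difference | One-sided error | P(claim) at planned rates |
|---|---|---|---|---|
| unchanged | 1.25 / 0.91 | 5.00 | 2.50% | 86.34% |
| doubled, both arms | 2.45 / 1.78 | 4.86 | 2.71% | 86.15% |
| halved, both arms | 0.63 / 0.46 | 5.07 | 2.40% | 86.44% |
| doubled, IA only | 2.45 / 0.91 | 4.41 | 3.51% | 88.50% |
| doubled, EA only | 1.25 / 1.78 | 5.46 | 1.90% | 83.69% |

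Deleted counts are at the margin rates; the last column uses 8.0% and 13.3%. With SSI-free loss of 3%, 5% or 10% and onset over days 3–20, 3–10 or 10–28, the last four errors range over 2.57–3.05%, 2.26–2.46%, 2.84–5.55% and 1.25–2.26%. If the plan's 20% drop-out allowance were all loss between days 7 and 30 (c = 0.800 and 0.672, onset days 3–20), doubling gives 3.4% (both arms), 8.4% (IA only) and 0.8% (EA only).

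**One record near the margin** (Wald upper 95% limit, in points). 20/175 v 23/175: −1.71 + 1.96×3.51 = 5.16, not met. Delete one IA SSI (19/174): 4.60, met. Delete one EA SSI (22/174): 5.61. Far from the margin it does not matter: 14/175 v 23/175 gives 1.28, and 0.68 after one IA deletion.

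**Counting recorded SSIs but dropping event-free non-completers** (5% loss). The share of SSIs recorded before loss is 0.989, so q = 18.91% and 13.77%, difference 5.14, error 2.3%. If every SSI is recorded: 5.18, 2.3%. This is slightly conservative.

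**The case against.** The strongest reply is that the sponsor meant only patients of unknown status. The endpoint and the CDC definitions in Attachment 1 turn on onset within 30 days, SAP 5 governs missing endpoint data, and a recorded SSI is not missing. That is a sensible reading and may be the intended one. SAP 4.5, however, defines what is missing, and does so by completion of follow-up.

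Second, not imputed and shown in tables amounts to a workable available-case rule, whatever word is used. That is fair, but an available-case rule is the deletion described here.

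Third, loss should be small. Protocol 12.3.2 expects little missing data, missed visits are rescheduled (7.3), patients are blinded (6.2) and the DSMB reviews loss yearly (12.6). Suspected SSI triggers imaging, so SSI patients may be followed more closely, which is the slightly conservative halved case. All of this stands as a limit on size. It does not restore a deleted event, and the same plan allows for 20% drop-out.

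Two stronger readings are not supported. A reader might infer that the protocol contradicts itself on what completion means, since the abstract says "patients are required to return to the hospital for blood routine" and other tests while 7.3 says "Follow-up will be conducted through in-patient observation, outpatient consultations, and telephone inquiries". Both places contain telephone contact and a day-30 CT, so they do not conflict; complete is merely undefined. A reader might also infer that the rule favours IA. Nothing in the documents gives loss by arm or by SSI status. Surgeons are unblinded and exit criterion 5 is open-ended, so differential loss is possible, but no passage indicates it.

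**Conclusion.** The point holds as a defect in a stated rule. Read literally, SAP 4.5 and 5, reinforced by exit criterion 5 and the mITT exclusion, let documented primary events leave the analysis. That the text gives no exemption is certain; that events would in fact be dropped is not.

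Direction and size are unknown and rest on assumed loss. There is no bias if loss is unrelated to SSI, and a small one if it is related equally in both arms at modest loss. It is material only if loss differs by arm, loss is far above what the protocol expects, or the result lies close to the margin. This should be fixed, but it does not undermine the design.

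**What to change.** Before unblinding:

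1. **SAP 4.5.** State: *Any SSI documented by day 30 counts as an event whether or not follow-up was completed; only patients with no SSI at last contact before day 30 have a missing endpoint.* Define complete as SSI status known to day 30 by any planned contact route. Give a rule for death before day 30 without SSI and report such deaths by arm.
2. **SAP 5 and protocol 12.3.2.** Replace the censoring term for SSI with a defined rule. The planned risk difference can stay, because dropping event-free non-completers while counting all SSIs is only slightly conservative. Add one sensitivity analysis that retains those patients, for example a Kaplan–Meier 30-day risk difference or a tipping-point analysis. Changing the primary estimator is optional.
3. **Protocol 5.3, 7.4 and 12.2.1 and SAP 4.2.1.** Reconcile them so that incomplete follow-up alone does not remove a patient from mITT, subject to withdrawal of consent for data use.

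Cost: a few sentences and modest programming, with N unchanged at 350. Protocol 13.1 lists eCRF content only as endpoints and baseline data, so the sponsor should confirm that SSI and last-contact dates are held there or can be taken from source records.
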